## 6. Subgroup Analysis

Subgroup analyses for the primary efficacy outcome will be performed on the ITT population in order to explore whether the treatment effect is consistent across subgroups. Our goal is to determine the impact of PARTICS on asthma exacerbations in two pre-specified main subgroups determined by 1) race/ethnic group (African American vs. Hispanic/Latino) and 2) smoking status [i.e., participants who are previous (>10 pack- years)/current (or within 1 year) smokers vs. those who have not smoked (in the past year and <10py)] 3) patients with high FeNO vs. low and 4) patients with high eosinophil counts vs. low. Based on our prior experience, about 50% of our population will be smokers or ex- smokers.

Subgroup analyses to evaluate variation in treatment effect will be performed on the basis of tests for interaction using the same Andersen-Gill version of the Cox proportional hazards model as used in the primary analysis. The model will be including terms for treatment arm, subgroup, and treatment by sub-group interaction and adjust for all variables included in the primary model. Additionally, treatment effects within each categorical subgroup will be examined separately using analogous Andersen-Gill model. Event rates by treatment arm and hazard ratios with 95% confidence intervals will be reported for each subgroup. Forest plots will be generated displaying the estimated hazard ratios and 95% confidence intervals for each subgroup will be presented. Variation in treatment effect will be assessed on the basis of tests for interaction in the Andersen-Gill version of the Cox proportional hazards model described above. Treatment effects estimated within each categorical subgroup will be considered exploratory/hypothesis generating. Thus, no adjustment for multiple testing will be employed.

Additional exploratory subgroup analyses will be performed investigating the effect of the following factors: 1) modality in which questionnaires have been returned; 2) patients' attitude towards ICS from the validated BMQ (skeptical (low necessity, high concerns), indifferent (low necessity, low concerns), ambivalent (high necessity, high concerns), accepting (high necessity, low concerns)); 3) presence of depressive symptoms (yes/no); 4) health literacy status (low or marginal versus high); and 5) patient adherence barriers from the validated ASK12 questions 1,2,3 and 11 related to measures of inconvenience, forgetting and

cost.

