All patients (both PARTICS and control groups) will be asked to complete monthly questionnaires using validated instruments to assess exacerbations, symptoms, medical visits primarily driven by asthma (visits, ED visits, and hospitalization) and medication use. At enrollment, patients will choose how they wish to primarily complete the questionnaire (online, smart phone, mailed—exactly same questions and multiple-choice answers for each method). Monthly reminders to complete each monthly survey will be sent to patients through all methods of communication that the patient provides (text, email, phone call). Patients will be allowed to change methods whenever requested. Several of the instruments have been validated to be comparable across these response methods (Schatz 2007a, Schatz 2007b, and Schatz 2007c). In addition to monthly survey reminders, patients will also receive quarterly reminder text messages about the study and monthly surveys. Patients may opt out of the text messages at any time.

Before sites begin enrolling patients, the study team will host centralized training for the site PI and key practice personnel, and all clinic team members will be instructed about the overall study protocol and the PARTICS approach.

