#### **5. Blinding/medications**

In keeping with a pragmatic trial, this will be an unblinded trial. Since the strategy is patient-activated, we will not enroll more than one patient per household. After knowing the treatment arm randomized to, each patient will watch a video that instructs him/her on how to get the medication he/she is assigned to receive. Although each individual patient or site investigator could know the randomized treatment arm a patient is assigned to, the randomization scheme for the full study will be kept confidential from all the investigators. Randomization scheme will be generated by the unblinded statistician at Duke Clinical Research Institute, and will be implemented by an authorized party who has no involvement in the conduct of the study. This blinding measure aims to eliminate any possibility that the study data is viewed aggregate by randomized treatment before the completion of the trial by anyone outside of the DCRI unblinded statistical team. In order to ensure all the study investigators are unbiased when making decisions during the conduct of the study, it is important to keep them blinded about the possible study results by treatment.

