- o Participants will be asked to participate in short phone calls to assess ability to follow study instructions and study processes at 1, 6, and 12 weeks (see **Appendix C**).
- **Full study difference:** There will be no phone calls to assess ability to follow study instructions and study processes at 1, 6, and 12 weeks. In addition, the Full study will have up to 15 months of follow up questionnaires versus 3 months in the Vanguard.
  - o At 26, 28 and 30 days they will receive reminders to complete the next monthly survey through all available methods provided by the patient, until they have completed their survey.
  - o At day 27, the local site study coordinator will call the patient to make sure s/he received the monthly survey reminder.
  - o If they have not completed their survey by day 32, they will be added to a list for the central research team to call and help them complete the process either immediately over the phone or by having them engage their preferred completion method.
  - o If the telephone follow-up process does not produce an adequate response, we will consider mailing a paper survey to patients who do not respond
  - o Each monthly survey sent to patients will be based on 30-day periods starting from the Baseline survey. The first month survey will be sent at 30 days, the second month survey will be sent at 60 days, and so on.
  - o We completed African American enrollment. We are extending Hispanic/Latino enrollment for 3 months until April 30, 2020, but not extending the project period. If a patient is enrolled in February 2020, they would be followed for 14 months, March for 13 months, April for 12 months.

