### **3. Methodology for Collecting Patient Consent and Questionnaire Data**

The Patient Engaged Electronic Reporting System (PEERS) has been developed and enhanced over the past 15 years by the University of Colorado, Department of Family Medicine (CUDFM.) The system is licensed to the DARTNet Institute and will be customized and provided to the study through a purchased services agreement between the AAFP and DARTNet. The system is a HIPAA compliant, multi-modal, fully localized patient data collection and study management system. The system is used for both clinical care and research. The system is a table driven data collection system with advanced within questionnaire data management as well as between questionnaire data management. Many of the advanced features will not be necessary for this project.

At enrollment, following consent, patients will provide all available contact methods (phone number, email, text) and will receive reminders on all methods provided. All messages are HIPAA compliant (no clinical information is included) and provide a link to the appropriate login system (browser/mobile browser for email or text message and interactive voice response system for phone messages.) Patients may move between data collection systems as they wish.

PEERS is hosted in the CUDFM data center (which also serves as the HIPAA compliant data center for all DARTNet activities.) This center is secured environment with 24 hour police monitoring, password controlled entry that is monitored as well as both local and central police alerts for open/ajar doors. The entire center is located behind the University of Colorado Palo Alto firewall with advanced intrusion detection software and monthly remote server auditing for security. The data environment is located behind a second, research/clinical firewall maintained by the CUDFM informatics staff. All data transmissions for end users are encrypted. The CUDFM maintains daily incremental back-ups, weekly system images and monthly full file level back-ups. Off- site and cloud back-up storage is maintained with a 12-month rotation system.

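### The exploratory subgroup by return modality rests on a variable known only from follow-up, so its interaction test may not preserve the randomised comparison

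*Combined protocol and SAP*

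**What the plan says.** Section III.E.6 (Subgroup Analysis) places the "modality in which questionnaires have been returned" first in its list of additional exploratory subgroup factors. Part II, item 3 (Participant subgroups, full study only), names the same factor and defines it no further. Section III.E.6 runs subgroup analyses of the primary outcome in the ITT population, using a treatment-by-subgroup interaction in the Andersen-Gill model and hazard ratios by stratum. It names no other method for the exploratory list, so I take that model to apply.

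The passages on data collection bear on how the variable arises:

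- Part II, Full study differences: "At enrollment, patients will choose how they wish to primarily complete the questionnaire". The same paragraph adds: "Patients will be allowed to change methods whenever requested".
- Methodology for Collecting Patient Consent and Questionnaire Data: "Patients may move between data collection systems as they wish".
- Follow-up Intensity, full study: "If they have not completed their survey by day 32, they will be added to a list for the central research team to call". The sentence goes on to allow completion either during that call or by the method the patient favours. If telephone follow-up does not succeed, "we will consider mailing a paper survey to patients who do not respond".
- Blinding/medications: "this will be an unblinded trial".

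**The concern.** A subgroup analysis compares randomised groups within each stratum if stratum membership is fixed before allocation. Return modality is not fixed then. It accumulates over 12 to 15 months of surveys, and patients who know their arm may change it. It can also change because a survey was late, and lateness may be related to how the asthma is going. If membership depends on arm and on events, the arms being compared within a stratum need not be alike at baseline. A difference between modalities could then reflect selection and be read as variation in the effect of PARTICS or in how well events are captured.

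There is also a gap in definition. The plan does not say how to classify a patient who used more than one method, and a patient who returned no monthly survey has no value at all.

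**Working it through.** No sample size, power or alpha figure in the plan depends on this factor, so there is no stated figure to reproduce. The check has two parts.

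**1. The passages side by side.**

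- *Timing.* The factor is observed during follow-up. The other exploratory factors in III.E.6 are baseline measures: the questionnaire schedule for the full study collects the BMQ, PHQ-2 and health literacy at baseline only, and III.E.2 tabulates ASK-12 with the baseline data. Modality is the exception.
- *Routes by which it can change.* There are three: patient request, completion during the staff call after day 32, and a possible paper survey. Only the first is unconditional.
- *Classification.* III.E.10 (Addressing missing data) lists seven ways to respond: mail, email, telephone, text, smartphone app, website and voice response. No rule maps a mixed history to a stratum. The same section continues to collect the primary outcome from records, claims and refills for patients who do not return questionnaires, unless they withdraw consent. A patient with no survey can thus contribute events to the ITT population and still have no stratum.
- *Alternative.* A primary method is chosen at enrolment. The documents do not say whether this happens before or after randomisation at that visit, or whether it is stored as a data field.

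**2. An illustration of possible bias.** Two inputs follow the plan's design assumptions in III.E.8: a control mean of 0.4 × 1.25 = 0.5 events per patient over 15 months, and a design rate ratio of 1 − 0.235 = 0.765. All other inputs are assumed. For each patient:

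- events Y follow a Poisson distribution with mean 0.5 × k × (rate ratio if PARTICS), where k is gamma frailty with shape 1 and mean 1;
- phone is chosen at enrolment with probability 0.30;
- the log-odds of moving to phone are −1 + g × min(Y, 3) + b × (1 if PARTICS), with g = 0, 0.5 or 1.0 and b = 0 or −0.6;
- returned modality is phone if phone was chosen or the patient moved to it.

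The interaction ratio is the rate ratio in the phone stratum divided by the rate ratio in the other stratum. The true ratio is the same in everyone, so an unbiased analysis gives 1.00. Each scenario used 2,000,000 simulated patients and crude rates, without censoring or covariates.

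| True rate ratio | g (events) | b (arm) | Enrolment choice | Returned modality |
|---|---|---|---|---|
| 1.0 | 0 | 0 | 0.992 | 0.995 |
| 1.0 | 0 | −0.6 | 0.995 | 0.996 |
| 1.0 | 0.5 | 0 | 1.006 | 1.002 |
| 1.0 | 0.5 | −0.6 | 0.998 | 0.997 / 1.086 = 0.918 |
| 1.0 | 1.0 | 0 | 1.000 | 1.002 |
| 1.0 | 1.0 | −0.6 | 1.005 | 1.031 / 1.159 = 0.890 |
| 0.765 | 0 | 0 | 0.997 | 0.996 |
| 0.765 | 0 | −0.6 | 1.001 | 0.999 |
| 0.765 | 0.5 | 0 | 1.002 | 0.764 / 0.782 = 0.977 |
| 0.765 | 0.5 | −0.6 | 1.000 | 0.759 / 0.841 = 0.903 |
| 0.765 | 1.0 | 0 | 0.989 | 0.766 / 0.799 = 0.958 |
| 0.765 | 1.0 | −0.6 | 1.004 | 0.786 / 0.931 = 0.844 |

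The enrolment choice stays at about 1.00 throughout. Returned modality does so when switching is unrelated to events. With no true effect, it departs from 1.00 only when switching depends on both events and arm. With a true effect, dependence on events alone already gives a small departure, because the arm itself changes the number of events.

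**The case against.** The strongest reply is that little depends on this. The factor is one of several exploratory ones, III.E.6 labels within-subgroup effects as hypothesis generating, and the primary analysis, the main subgroups and the power calculation do not use it. That stands and sets the severity. It does not remove the point, because the exploratory label limits the strength of a claim without restoring a randomised comparison.

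A second reply is that the team's interest in modality is response and reporting bias, for which the mode actually used is the more direct variable. That also stands as a trade-off. It argues for keeping actual return mode in a descriptive table, not for using it as a stratifier of the treatment effect.

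Four stronger readings are tempting, and the documents support none of them:

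- A reader might infer that everyone called after day 32 changes modality. The plan lets them complete by their favoured method, and paper is only considered.
- A reader might infer that the randomised comparison is certainly lost. The plan shows only that modality can depend on arm and asthma course; several scenarios above show no bias.
- A reader might take the earlier BELT trial's survey completion as a measure of how many patients are affected. The plan reports completion above 75% there, using paper and phone only. That does not count patients who switch method, or who return nothing, in this trial.
- A reader might assume that the enrolment choice is already stored and precedes allocation. Neither is stated.

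**Conclusion.** The point holds as a minor one. As written, the subgroup is defined after randomisation in an open-label trial, can depend on arm and asthma course, and leaves some ITT patients unclassified. Its interaction test may therefore not preserve the randomised comparison. Bias is possible, not certain, and its size cannot be quantified from the documents, which give no data on switching. The range of about 1.00 to 0.84 shows only what the assumed switching rules would produce. The conclusion about definition and timing rests on the text alone and does not need the simulation. Nothing beyond this one exploratory analysis is affected.

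**What to change.** In III.E.6 and in the Part II list of participant subgroups, define this factor as the primary completion method chosen at enrolment, provided it was captured before allocation was revealed. Report actual return modality descriptively by arm, counting surveys by method so that mixed users need no single label, with a separate line for patients who returned none.

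Before making the change, check in the data collection system whether the enrolment choice was stored and how its time compares with randomisation. If it was not stored, or came after allocation, drop the interaction test and report modality descriptively only. The choice cannot be collected retrospectively: the plan describes African American enrolment as complete and Hispanic/Latino enrolment as ending on April 30, 2020.

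The cost is an edit in two places, one check of the database and one descriptive table. Sample size, alpha and the primary analysis do not change. The downside is that enrolment choice addresses the effect of reporting mode less directly than the mode actually used; the descriptive table covers that question.

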## 7. Exploratory Analyses

In addition to the exploratory subgroup analyses mentioned above, we will also explore whether patient characteristics such as BMI, ICS/LABA use vs. ICS use, co-morbidity (such as history of heart disease, cancer, stroke, diabetes, chronic kidney disease, COPD/emphysema/chronic bronchitis, HIV/AIDS, and hypertension), and prior exacerbations (e.g., exacerbation within 12 months prior to randomization) affect the apparent effectiveness of PARTICS by examining the interaction of these factors with treatment. In addition, we will explore whether self-perceived discrimination affect outcomes regardless of treatment assignment.

The effect of provider adherence and patient adherence on the effectiveness of the PARTICS intervention will also be investigated. We will collect information from patients regarding their medication use and have added “non-invasive” ways to monitor what actually happens after they are randomized to either the enhanced usual care group or the intervention group. To this end, we will collect and incorporate the following into our descriptive information and into our exploratory analyses: 1) Information on the refills of the ICS in PARTICS “non-invasively” through the renewals at the pharmacy; 2) Information on PARTICS “adherence” by cross-referencing the ICS data above with patient monthly report of usage on their questionnaires and SABA pharmacy fulfillment data if available; 3) Information on PARTICS effects on other asthma medication use by comparing medication use between the intervention and non-intervention groups by examining monthly self-report and cross-referencing to pharmacy fulfillment data; 4) Measure of provider compliance with guidelines, by assessing whether providers adjust medications according to NAEPP guidelines. We will obtain this information “non-invasively” by examining EHR medication prescribing information at asthma related visits (none required by study). For each of these visits, we will refer to the patient’s self-reported asthma control score of the prior month (provided by the patient monthly questionnaire). We will examine medication prescribing at that visit from the EHR to assess the frequency with which providers stepped up, or stepped-down, care according to guideline recommendations (NAEPP, 2007); Patient adherence and provider adherence between the two treatment groups will be compared.

The analyses on the exploratory outcomes will also be performed. The rate on asthma deteriorations will be reported by treatment groups. The composite endpoint of asthma deteriorations or exacerbations will be analyzed using the same Andersen-Gill version of the Cox proportional hazards model as used in the primary analysis. The Asthma APGAR data will be analyzed using the same mixed model approach as described above in the Asthma Control Test (ACT) score analyses.

Data on the Asthma Medication Ratio (AMR) during the follow-up months, the total health care utilization (i.e., total number of visits made to the enrolling sites, total number of ED visits, and total number of hospitalizations), and asthma related health care utilization (i.e., number of visits made to the enrolling sites, number of ED visits, and number of hospitalizations for which asthma is a first or second diagnosis) will be summarized. Differences between two randomized treatment groups on these variables will be compared using either t-test or Kruskal-Wallis test if full follow-up is available on everyone or Poisson or Negative Binomial regression models with time as an offset to account for differential duration of follow-up.

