**Study Aims:**

Working with patient & health system stakeholders, we will conduct a pragmatic real-life study in a population of African American and Hispanic/Latino adults disproportionately impacted by asthma.

**Specific Aim 1:** To assess whether a Patient Activated, Reliever-Triggered Inhaled CorticoSteroid (PARTICS) strategy can reduce asthma morbidity in this population.

- Our primary outcome will be asthma exacerbations which have been shown to be important to patients and healthcare stakeholders.
- Our secondary outcomes will include additional outcomes important to patients such as days lost from work or school, asthma control, and asthma related quality of life.

**Specific Aim 2:** To examine whether the effectiveness of a Patient Activated, Reliever-Triggered ICS (PARTICS) strategy differs between African American or Hispanic/Latino adults or by smoking status.

**Exploratory Aim:** To examine, whether particular patient clinical characteristics (e.g. prior exacerbations) or specific barriers to adherence (e.g. beliefs, depression) impact the effectiveness of a PARTICS approach in these populations.

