## **C. Participant Recruitment, Screening, Enrollment, and Follow-up**

### **1. Eligibility Criteria**

#### **INCLUSION CRITERIA**

- Black or Hispanic based on self-identification (Hispanic if identify as both)
- Male and female, ages 18-75 years
- Ability to provide informed consent
- Clinical history consistent with asthma for > 1 year.
- Prescribed ICS as daily maintenance therapy
- Participant must also have an ACT score of 19 or less, **or** a history of one or more exacerbations in the past year that required patient report of systemic corticosteroid use.

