#### **EXCLUSION CRITERIA**

- Life expectancy less than one year
- Known allergy to the ICS inhaler used in the study
- Having COPD or other chronic lung disease other than asthma; with the exception of the following:
  - Dx of COPD in a *never smoker* without any other lung disease or any other disease that might cause airway obstruction such as: Cystic Fibrosis, Connective Tissue Disease, premature birth, organ transplantation, bronchiectasis, sarcoid, and obliterative bronchiolitis
  - Dx of COPD in former smoker with normal PFTs done after the person quit smoking
  - Dx of COPD in current smoker with normal PFTs done in past 24 months

- Dx of COPD IN CURRENT OR FORMER SMOKER with obstruction on PFTs: normal diffusing capacity in past 24 months and demonstrated reversibility of 12% or more *at any time*
- Regular systemic corticosteroid use daily or every other day for any reason—including asthma or other medical reasons
- Use of systemic corticosteroid, or visit to the doctor's office, emergency department (ED) or urgent care, or overnight hospitalization for an asthma exacerbation in the past month (can wait and re-check eligibility after one month)
- Use of biologics (injections or infusion medicines): with the exception of the following:
  - the patient has been on a stable dose of a biologic for at least 6 months and,
    - must have had an exacerbation at least 2 months after starting on a biologic to be considered eligible **OR**
    - must have a current ACT score  $\leq 19$  to be considered eligible.
- Bronchial thermoplasty less than 6 months ago (can re-check eligibility 6 months after procedure)
- Another family member living in the same household already enrolled in study

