### **Asthma Control Test (ACT)**

The ACT is easy to use, patient completed, and assesses the frequency of shortness of breath, use of rescue medications, the effect of asthma on daily functioning, and overall self-assessment of asthma control. The ACT has been evaluated in independent study population samples and can be self-administered in person or at home (Schatz 2007a), by telephone (Schatz 2007b) and by mail (Schatz 2007c). The ACT has been recommended by the NAEPP and the NIH Asthma outcome workshop (NAEPP 2007, Cloutier 2012) because of the extensive validation data for these tools, using the widest range of criterion and construct measures, including demonstration of responsiveness to therapy and a minimal clinically important difference (MCID). The MCID is defined as the smallest difference in a given score of interest which *patients* perceive as beneficial and which would support a change in the patient’s *management* (Jaeschke 1989). The MCID for the ACT has been defined as 3 for individuals over time and between populations (Schatz 2009) and cut-off values for uncontrolled asthma:

ACT  $\leq$  19 (Nathan 2004), and “very poorly controlled” asthma: ACT  $\leq$  15 have been established. (Schatz 2006, Nathan 2004).

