### **4. Statistical Analysis for Primary Outcome**

The primary aim of the study is to determine the impact of PARTICS on asthma outcomes in a minority population consisting of African American and Hispanic/Latino adults. The primary outcome of this study will be the intensity of asthma exacerbations during the months of follow-up between those patients randomized to addition of PARTICS to provider-educated care vs. those who continue with provider-educated care alone.

Rate of asthma exacerbations per year will be reported for two treatment groups. Annualized rates of count outcomes will be summarized using the annualized mean occurrence based on the Poisson model.

Exacerbations rates during follow-up will be compared using the Andersen-Gill adaptation of time-to-event Cox proportional hazards model with robust standard errors to account for potential multiple occurrences of the outcome in each patient (Andersen Gill, 1982). This model was selected over the more commonly used time to first event Cox model for two reasons. First, we believe that total experience during follow-up matters more to patients than the onset of the first exacerbation. Second, the power is increased when multiple events can be included. The covariates in the primary comparison will include: study center (to account for any geographic variation in patterns of care), h/o exacerbations in the past year (y/n), on ICS/LABA prior to randomization (Y/N), race/ethnicity, smoking status (as defined for subgroups), age, BMI (body mass index), and gender since all may influence the rate of exacerbations or the response to corticosteroids. The primary effect will be based on the randomized treatment arm indicator

variable.

Time from randomization to first asthma exacerbation will be compared using the log-rank test. In addition, survival curves will be constructed for this time-to-event endpoint using Kaplan-Meier method.

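### Because entry requires ACT 19 or less or a past-year exacerbation, a treatment effect that differs by prior exacerbation cannot be attributed to exacerbation history alone unless baseline ACT is brought into the exploratory analysis

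*Combined protocol and SAP*

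**What the plan says.** All references are to the combined protocol and SAP.

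- **Entry (II.C.1, inclusion criteria).** The last criterion can be met in two ways. The first concerns current control: "Participant must also have an ACT score of 19 or less". The second is an alternative to it, concerns history, and applies whatever the ACT score: "a history of one or more exacerbations in the past year that required patient report of systemic corticosteroid use".
- **Biologic users (II.C.1, exclusion criteria).** The exception opens no third route. Such a patient either "must have had an exacerbation at least 2 months after starting on a biologic to be considered eligible" or qualifies on a current ACT of 19 or less, and the inclusion criteria still apply.
- **Meaning of the threshold (II.D.2, ACT).** A score of 19 or less is one of the "cut-off values for uncontrolled asthma".
- **Planned analysis.** The Exploratory Aim (I.A.2) is to examine "whether particular patient clinical characteristics (e.g. prior exacerbations", among other features, in relation to effectiveness. III.E.7 carries this out by testing each factor's interaction with treatment. For this factor the question is whether "prior exacerbations (e.g., exacerbation within 12 months prior to randomization) affect the apparent effectiveness of PARTICS".
- **Model.** III.E.7 sets out no separate model for these interactions. The interaction model in III.E.6 has treatment, subgroup and their product, plus the primary covariates. III.E.4 lists those covariates, including "h/o exacerbations in the past year (y/n), on ICS/LABA prior to randomization (Y/N), race/ethnicity, smoking status (as defined for subgroups), age". Baseline ACT is not among them, and no treatment-by-ACT term appears anywhere.
- **Data.** ACT is collected at baseline (II.D.2(b), full-study table) and summarized by arm (III.E.2).

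**The concern.** The entry rule leaves one cell empty by design: no prior exacerbation with ACT above 19. The group without a prior exacerbation is therefore wholly uncontrolled by the protocol's own cut-off, while the group with one can mix controlled and uncontrolled patients. The planned contrast between these groups varies exacerbation history and, to an unknown extent, current control.

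The protocol gives a reason to think control could modify the effect. Study ICS is taken puff for puff with the reliever (VII.B.1), and ACT includes rescue use among its items (II.D.2). Patients with better control may therefore take less study ICS. It is also plausible that some prior exacerbators score above 19: the second route admits them, and recent exacerbations are screened out for a month (II.C.1). These are grounds for plausibility, not evidence.

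At stake is how an exploratory result is read. VII.D.2 says the trial will show whether particular subgroups benefit more. A difference by prior exacerbation would naturally be read as a statement about exacerbation history.

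**Working it through.** **1. The plan's own subgroup power.** Inputs from III.E.8: control rate 0.4 per year, 15 months of follow-up, uniform loss of 31.25% over that time, two-sided 0.05.

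- Mean exposure = 1.25 × (1 − 0.3125/2) = 1.055 years.
- 300 per arm, 32% reduction: expected events 300 × 0.4 × 1.055 = 126.6 and 126.6 × 0.68 = 86.1. SE of the log rate ratio = √(1/126.6 + 1/86.1) = 0.140. Power = Φ(0.386/0.140 − 1.96) = 78.8%, against 80% stated.
- 600 per arm, 23.5% reduction: 253.1 and 193.6 events, power 80.1%.

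Both stated figures reproduce, and the same set-up is used in step 4.

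**2. Share with ACT 19 or less, from the entry rule**

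| Group | Share with ACT 19 or less |
|---|---|
| No qualifying prior exacerbation | 1, by design |
| Prior exacerbation | q, not given |

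This assumes that the analysis uses the same exacerbation definition and ACT reading as entry.

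**3. Spurious interaction if the effect depends on ACT only.** Let HRu and HRc be the treatment hazard ratios at ACT 19 or less and above 19. Let k be the control event-rate ratio of ACT 19 or less to above 19. The ratio of hazard ratios (prior exacerbation to none) is

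R = [(q·k·HRu + (1 − q)·HRc) / (q·k + 1 − q)] / HRu.

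For example, with q = 0.75, k = 1, HRu = 0.70 and HRc = 0.90: R = (0.525 + 0.225)/0.70 = 1.07. All four inputs are assumptions.

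| HRu, HRc | k | q = 1 | q = 0.9 | q = 0.75 | q = 0.5 | q = 0 |
|---|---|---|---|---|---|---|
| 0.70, 0.90 | 1 | 1.00 | 1.03 | 1.07 | 1.14 | 1.29 |
| 0.70, 0.90 | 2 | 1.00 | 1.02 | 1.04 | 1.10 | 1.29 |
| 0.70, 1.00 | 1 | 1.00 | 1.04 | 1.11 | 1.21 | 1.43 |
| 0.70, 1.00 | 2 | 1.00 | 1.02 | 1.06 | 1.14 | 1.43 |
| 0.85, 0.70 | 1 | 1.00 | 0.98 | 0.96 | 0.91 | 0.82 |
| HRu = HRc | any | 1.00 | 1.00 | 1.00 | 1.00 | 1.00 |

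The last row and the q = 1 column show that both conditions are needed. The fifth row shows that the direction can reverse.

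A simulation from one latent severity (assumed source ACT mean 18.5, SD 4.9, 0.35 exacerbations per year) gave q = 0.66. R was 1.12 for hazard ratios of 0.65 and 0.95, and 1.08 for 0.70 and 0.90.

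**4. Against the precision of the interaction.** Assume a 50/50 split by prior exacerbation, the III.E.8 inputs and a 23.5% reduction in both groups.

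- Each group has 126.6 and 126.6 × 0.765 = 96.8 events, so its variance is 1/126.6 + 1/96.8 = 0.0182.
- SE of the log interaction = √(2 × 0.0182) = 0.191.
- Ratio detectable with 80% power = exp[(1.96 + 0.84) × 0.191] = 1.71, or its reciprocal 0.59.
- A spurious ratio of 1.07 would be called significant 6.5% of the time, 1.14 about 11% and 1.21 about 17%, against 5% nominal.

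Overdispersion or an unequal split would raise the SE and lower these rates.

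**The case against.** A reader might infer that the interaction is confounded outright, that the exploratory aim will be answered wrongly, or that the missing ACT covariate weakens the primary comparison. The documents do not support these readings.

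- **Not aliased.** Prior exacerbators may also have ACT 19 or less, so the two factors overlap and can be separated with data already collected.
- **The planned test is valid for what it compares.** Treatment is randomized (II.C.3), so the contrast within each group is sound and the interaction tests whether the effect differs between the groups as enrolled. III.E.7 speaks of exploring apparent effectiveness and does not claim to isolate one cause.
- **Primary analysis untouched.** Omitting a prognostic covariate does not invalidate a randomized comparison.
- **Lowest tier.** Prior exacerbation is not among the four subgroup factors named in III.E.6, and that section treats within-subgroup estimates as hypothesis generating. The wording in III.E.7 leaves the coding open, and a contrast of one exacerbation against two or more would not involve the empty cell.
- **Small and assumption-driven.** The share above ACT 19 and the dependence on ACT are assumed, and the resulting ratios are far below what the trial can detect.

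All of this stands, and it limits the point to attribution. What survives is that calling an analysis exploratory does not tell its reader that the two groups differ in asthma control by design.

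Background text (II.A.1 and the discussion after the criteria in II.C.1) also names ICS/LABA use as marking at-risk patients. The formal criteria do not make it an alternative to the ACT or exacerbation condition, so it does not fill the empty cell.

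**Conclusion.** The point holds as a minor matter of interpretation. By the written criteria, every patient without a qualifying exacerbation has ACT 19 or less, and the model as specified cannot separate exacerbation history from current control. A difference could partly reflect control if two conditions hold: the effect varies with ACT, and a material share of prior exacerbators score above 19. The documents establish neither, and the distortion is exactly zero if either fails. With k = 1, q between 0.5 and 0.75, and hazard ratios of 0.70 against 0.90 or 1.00, the spurious ratio is about 1.07 to 1.21. It is smaller if uncontrolled patients have more events, and below 1 if controlled patients benefit more.

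**What to change.** In III.E.7, keep the full-population interaction as planned and add, before treatment-arm results are seen:

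1. A supplementary model with baseline ACT and treatment-by-ACT alongside prior exacerbation and its interaction. An ACT main effect alone would not be enough. Above ACT 19 only prior exacerbators contribute, so this model leans on the assumed form of the ACT effect.
2. The prior-exacerbation contrast repeated among patients with baseline ACT 19 or less, where both groups exist. Differences in control within that range may remain.
3. A sentence stating that the full-population contrast alone cannot be attributed to exacerbation history.

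**Cost.** SAP wording and two extra fits; no new data. The restricted contrast is less precise. With a 50/50 split and equal event rates, its SE grows by √[(1 + 1/q)/2]: 8% at q = 0.75 (0.191 to 0.206) and 22% at q = 0.5 (0.191 to 0.234).

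**Optional.** Baseline ACT could join the III.E.4 covariates for a small precision gain. In 300 simulated trials of 1,210 patients, the variance of the treatment effect fell by about 1% (ratio 0.986). The change would carry into III.E.5 (including the analysis of ACT change itself), III.E.6 and the composite outcome in III.E.7. It would not by itself resolve the interaction.
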